#### 7.5.1 Clinical endpoints

- 1. Impact of test result on prescribing, specifically:-
  - (a) Time, from admission to MAU, to first administration of 'narrow-spectrum' antibiotics, for patients in Groups 1, 2, and 3, who are prescribed antibiotics.
  - (b) Time, from admission to MAU, to first administration of oral antibiotics, for patients in Groups 1, 2, and 3, who are prescribed antibiotics
  - (c) Time (hours) from admission to MAU to prescription of 'no antibiotics' (oral or intravenous) administered to patients in Groups 1, 2, and 3, who have influenza or RSV.
  - (d) Proportion of patients with influenza in Groups 1, 2, and 3 who are prescribed neuraminidase inhibitors.
- 2. Clinical outcomes, specifically:-
  - (a) *Length of hospital stay* until discharge:
    First, for all patients in Groups 1, 2, and 3.
    Second, for all patients with (i) influenza; (ii) RSV; and (iii) *S. pneumoniae* infection in Groups 1, 2, and 3.
  - (b) Fever duration (during the first 10 days of hospitalisation) Time from admission (hours) until the patient first became apyrexial (temperature ≤37.2°C), and remained so for a period of at least 24 hours:

First, in all patients in Groups 1, and 2 in comparison to Group 3.

Second, in patients with S. pneumoniae in Groups 1, and 2, in comparison to Group 3.

(c) Supplemental oxygen dependence and CPAP dependence (during the first 10 days of hospitalisation) Times from admission (hours) until the patient required (i) no supplemental oxygen, and (ii) no CPAP, for a period of at least 24 hours: First, in all patients in Groups 1, and 2 in comparison to Group 3.

Second, in patients with S. pneumoniae in Groups 1, and 2, in comparison to Group 3.

- (d) Admissions to Intensive Care (during the first 10 days of hospitalisation):
  First, the proportion of patients with *S. pneumoniae* infection in Groups 1, 2, and 3.
  Second, to better define the burden of influenza and RSV, the proportion of all patients with (i) influenza, and (ii) RSV who require ITU support.
- (e) *Ventilatory support* (during the first 10 days of hospitalisation):
   First, the proportion of patients with *S. pneumoniae* infection in Groups 1, 2, and 3.
   Second, to better define the burden of influenza and RSV, the proportion of all patients with (i) influenza and (ii) RSV who require ventilatory support.
- (f) *Deaths* (within 28 days of hospitalisation):
  First, the proportion of patients with *S. pneumoniae* infection in Groups 1, 2, and 3.
  Second, to better define the burden of influenza and RSV, the proportion of all patients with (i) influenza, and (ii) RSV, who die.
- 3. Quality of life, as measured by EuroQol, and quality adjusted life years generated during the 28 days after admission, will be assessed:
  - (a) In all patients in Groups 1, and 2 in comparison to Group 3.

- (b) Second, in patients in patients with (i) influenza, (ii) RSV, and (iii) *S. pneumoniae* in Groups 1, and 2, in comparison to Group 3.
- 4. Use of isolation facilities
  - (a) The time from admission to the MAU to the time of admission to a single room (isolation cubicle) will be compared for patients with confirmed influenza or RSV in Groups 1, 2, and 3.
  - (b) The proportion of patients with influenza or RSV in Groups 1, 2, and 3 who are isolated at any stage during the first 120 hours of the admission.
  - (c) The proportion of patients with *S. pneumoniae* infection in Groups 1, 2, and 3 who are inappropriately isolated for >12 hours.

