	
 
Have an acute exacerbation of chronic cardio-pulmonary illness of ≤168 hours (7 days) duration, OR an acute cardio-pulmonary illness or influenza-like illness of ≤7 days duration, including:         
 
Pneumonia,
 
Influenza/influenza-like illness,
 
Exacerbations of chronic obstructive pulmonary disease (COPD),
 
Bronchitis,
 
Asthma,
 
Congestive heart failure,
 
Cardiac arrhythmia;
 
 
 
Able and willing to adhere to the procedures stated in the protocol
 
Patients should have access to a telephone
 

Exclusion criteria	
 
Inclusion criteria not met
 
Angina/suspected myocardial infarction;
 
Were recruited to this study within 28 days of the current admission
 
Could not be recruited into the study within a 16-hour period of initial assessment by a doctor on the Medical Admissions Unit or a ward accepting acute medical admissions;
 
Enrollment in a study of antimicrobial therapy for the illness for which the patient was admitted
 

Randomisation:	Patients in each centre will be randomly allocated to one of three diagnostic policy groups: Group 1: Near patient tests (Quidel – influenza; Binax NOW – pneumococcus); Group 2: rapid molecular tests ('flu & RSV plus laboratory testing of concentrated urine in the Binax NOW assay); and Group 3: traditional laboratory culture, using computer generated randomisation codes stratified by centre.
Assessment methods:	
 
Clinical
 
Impact of test result on prescribing, specifically:- 
 
(a) Earlier use of 'narrow-spectrum' anti-microbial therapy,
 
(b) Earlier switch from intravenous to oral therapy,
 
(c) Avoidance or earlier discontinuation of antibiotics in patients infected with influenza and RSV, and
 
(d) Prescriptions of influenza neuraminidase inhibitors
 
Will be assessed in rapid near patient (Group 1) and molecular diagnostic groups (Group 2) and compared to traditional laboratory culture (Group 3).
 
 
 
2. Clinical outcomes, specifically:- 
 
(a) Length of hospital stay;
 
(b) Fever duration,
 
(c) Supplemental oxygen dependence and CPAP dependence,
 
(d) Deaths
 
Will be assessed in rapid near patient (Group 1) and molecular diagnostic groups (Group 2) in comparison to traditional laboratory culture (Group 3).
 
 
 

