It is possible that patients with a positive rapid pneumococcal antigen test result may receive a single antimicrobial agent, and that mortality of patients with polymicrobial infection including S. pneumoniae is increased. Oosterheert *et al* recently undertook a systematic review to assess whether treatment with a  $\beta$ lactam plus macrolide or quinolone monotherapy is truly superior to beta-lactam treatment alone. Eight relevant studies were selected. In six, significant reductions in mortality were found; in one, a reduction in hospital length of stay was found; and in another no beneficial effects could be demonstrated for treatment regimens with fluoroquinolone monotherapy or combinations of  $\beta$  -lactams and macrolides. The studies supporting the recommended treatment regimen were designed as non-experimental cohort studies. As a consequence, confounding may have influenced the results. In addition, the outcomes showed several inconsistencies. The authors concluded that a randomised controlled trial is warranted to circumvent the methodological flaws in the designs of the currently available studies, particularly as the addition of macrolides or treatment with fluoroquinolones may lead to enhanced antibiotic resistance, increased side effects, and healthcare-related costs. In Leicester, the recommended empiric therapy for patients hospitalised with CAP consists of monotherapy with a β-lactam agent or erythromycin if allergic to penicillin. Addition of a macrolide is not recommended unless the pneumonia is severe and therapy is adjusted 'as appropriate' at 48 hours if there has been no improvement. Although the available evidence does not indicate that rapid near patient pneumococcal antigen testing will adversely affect patient outcome, we plan that an independent Data Monitoring Committee conduct interim analyses to ensure that patient welfare is not adversely affected.

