#### **2 OBJECTIVES OF THE STUDY**

#### 2.1 Research objectives and hypotheses

In the Medical Admissions Units/Wards of the University Hospitals of Leicester, to:

1. Determine the diagnostic accuracy (sensitivity, specificity, positive and negative predictive values) of rapid molecular and near patient diagnostic tests for influenza, RSV and *S. pneumoniae* infections in comparison to traditional laboratory culture.

The increased diagnostic accuracy of rapid molecular and near patient tests over traditional laboratory methods improves patient management through better use of antimicrobials and isolation facilities. Rapid molecular and near patient diagnostic tests for influenza, RSV and S. pneumoniae infections are more cost-effective than traditional laboratory diagnostic tests.

2. Assess the potential benefits of ease of use, and speed of rapid molecular and near patient diagnostic tests for influenza, RSV and *S. pneumoniae* infections, in comparison to traditional laboratory culture.

Rapid molecular and near patient diagnostic tests for influenza, RSV and S. pneumoniae infections provide benefits in terms of (a) ease of use, and (b) more rapid results, in comparison to traditional laboratory culture.

3. Determine whether rapid molecular and near patient diagnostic tests for influenza, RSV and *S. pneumoniae* infections have any impact on prescribing.

Rapid molecular and near patient diagnostic tests for influenza, RSV and S. pneumoniae infections result in earlier use of narrow-spectrum antimicrobial therapy; and/or an earlier switch from intravenous to oral therapy; and/or earlier discontinuation of antibiotics in patients infected with influenza and RSV - in comparison to traditional laboratory culture

4. Determine whether rapid molecular and near patient diagnostic tests for influenza, RSV and *S. pneumoniae* infections allow more appropriate use of isolation facilities, in comparison to traditional laboratory culture.

Rapid detection of influenza and RSV by rapid molecular and near patient diagnostic tests leads to the appropriate isolation of patients, but only in hospitals/wards with an adequate provision of cubicles.

5. Compare the costs of performing rapid molecular and near patient diagnostic tests for influenza, RSV and *S. pneumoniae* infections, in comparison to traditional laboratory culture.

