the different microbiological tests for influenza, RSV, and *S. pneumoniae*, together with the results, will be documented

*Treatment* The nature (name, dose, frequency, and route of administration) of all antimicrobials given to all patients within 10 days of admission will be documented. Note will be made of when 'broad-spectrum' treatment is switched to 'narrow-spectrum treatment'; when intravenous antibiotics are switched to oral therapy; and when antibiotics are discontinued. The requirement for supplemental oxygen will also be documented.

*Isolation status, admission to ITU, and ventilatory support* A record will be kept of (i) the patient's isolation status during the first 7 days of admission, and whether the patient was admitted to an ITU and/or required ventilatory support (including ward-based CPAP) during the first 10 days of admission.

*Pyrexia* The time (24 hr clock and date) during the patient's first 10 days of hospitalisation (or until death, if relevant) when the patient first became apyrexial (temperature  $\leq 37.2^{\circ}$ C), and remained so for a period of >24 hours will be recorded.

*Convalescent serology* A convalescent blood sample will be collected for paired acute and convalescent serology for influenza and RSV at 10 -90days.

*Diagnostic studies* The nature and results of all diagnostic studies (e.g., chest radiograph, ECG, full blood count, cardiac enzymes, PaO2) carried out by the medical team will be recorded.

*EuroQol* The health status of all patients will be assessed by the EuroQol on days 7 and 28. Where patients have been discharged the EuroQol will be assessed by telephone interview of the patient or by postal questionnaire or by proxy (Appendix I).

*Humoral and cell-mediated immunity to the pneumococcus.* Patients whose antigen tests for the pneumococcus are positive and an equivalent number of people whose pneumococcal test is negative will be bled on one occasion only within 5 days of hospital admission, for tests of cellular and humoral immunity to the pneumococcus.

Physical Activity Questionnaire will be completed on day 2 or 3.

*Deaths* Deaths that occur within a maximum 28 days of hospitalisation will be identified by the study nurse and recorded in the CRF. [Note: the principal investigator MUST be notified by the study nurse of all deaths that occur within 28 days of admission and of the patient's study group].

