## 6.2.2 Monitoring antimicrobial and antiviral treatment (Days 2, 3, 4,5,6 7,8,9, 10, and 28), and other new drugs prescribed for this illness

- The relationship between the results of diagnostic tests and antimicrobial therapy is a key measure. The study nurse will record the name(s), the time when first administered, the dose, frequency of administration, and route of delivery of all newly prescribed antimicrobials/antivirals in the CRF. Subsequent changes in dose, frequency of administration, and route of delivery must be documented, even when the same antimicrobial is prescribed. The number of days that each formulation was prescribed will be documented in the CRF by reference to the Prescription Chart.
- 2. The nature of antibiotic, i.e., whether 'narrow/targeted' or 'extended'-spectrum, will be entered subsequently in the CRF.
- 3. Resource use is a key measure in this study, so the name(s), dose, frequency, and route of administration of newly prescribed drugs (including routinely prescribed medication at a higher dose, such as insulin) and intravenous fluids will be recorded in the CRF, by reference to the Prescription Chart.
- 4. The name(s), dose, frequency, and route of administration of any newly prescribed antimicrobial drugs that are given to the patient on discharge will be recorded in the CRF by reference to the Prescription Chart.
- 5. Details of any antibiotics prescribed for this condition by the GP following discharge will be captured by a Questionnaire (Appendix I, see Pages 60 and 65). Patients will receive a reminder telephone call on Day 28 to return the Questionnaire by post.

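### Endpoint 1(b) times the first oral antibiotic dose in everyone prescribed antibiotics, but the hypothesis it serves is an earlier switch from intravenous to oral therapy

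*Protocol*

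**What the plan says.** Section 7.5.1, item 1(b), repeated in the Synopsis list of endpoints, fixes the event as "Time, from admission to MAU, to first administration of oral antibiotics" and the population as all patients in the three groups with an antibiotic prescription. It sets no condition that IV drugs were given first, have stopped, or stay stopped.

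The hypothesis under objective 3 in Section 2.1 is "earlier use of narrow-spectrum antimicrobial therapy; and/or an earlier switch from intravenous to oral therapy", each in comparison with laboratory culture. The Synopsis assessment methods, item 1(b), read "Earlier switch from intravenous to oral therapy".

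The data for a switch are collected. The treatment paragraph of Section 4.1 says a note will be made of "when intravenous antibiotics are switched to oral therapy; and when antibiotics are discontinued". Section 6.2.2, item 1, also requires later changes of route to be documented.

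Two neighbouring endpoints in Section 7.5.1, fever (2(b)) and oxygen/CPAP (2(c)), count only a state that lasts at least 24 hours. The antibiotic endpoints carry no such rule. Section 7.6 analyses the antibiotic times by survival methods and describes the event as a prescription, whereas Section 7.5.1 describes it as an administration.

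**The concern.** A first oral dose and a switch from IV to oral are different events. They coincide only when a patient starts on IV, then goes on to oral drugs, and IV stops at that point. For everyone else the endpoint records something the hypothesis is not about.

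Section 6.2.2 calls the relation between test results and antimicrobial therapy a key measure of the trial. If many events in 1(b) are settled by the initial regimen, the comparison between groups is diluted. A null result could then be read as showing that rapid results do not change the route of treatment, when the endpoint was largely not observing that change. Section 7.4 gives no power for any prescribing endpoint, so no stated margin absorbs the loss.

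**Working it through.** The plan states no figure for this endpoint, so there is none to reproduce. The check sets the definition against the hypothesis, patient by patient.

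| Course of treatment | Endpoint 1(b) as written | IV-to-oral switch |
|---|---|---|
| IV, then oral with IV stopped | Event at first oral dose | Same time |
| Oral from the start, never IV | Event at first oral dose | Cannot occur |
| IV plus an oral drug, IV continues | Event at first oral dose | Not yet; occurs when IV stops |
| IV, one oral dose, back to IV within a day | Event stands | Depends on a persistence rule, which is not given |

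Rows two and three are direct mismatches. Row four is a gap in the definition; the hypothesis itself does not demand a sustained switch.

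**Can these courses arise?** Row two can, because the population is anyone prescribed antibiotics, by any route. Row three can, because Section 1.5 describes UK empirical treatment for pneumonia as a beta-lactam with or without a macrolide. The same section says local guidance keeps the added macrolide for severe pneumonia: "Addition of a macrolide is not recommended unless the pneumonia is severe and therapy is adjusted 'as appropriate' at 48 hours". For pneumonia, therefore, row three may be less common than row two. No frequencies are given.

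**Can the event precede a test result?** Yes. The clock starts at admission to the MAU. Section 4.1 allows recruitment up to 16 hours after initial assessment, and Section 6.1.2 says the approach normally follows clerking by the admitting doctor. An oral dose given in that interval is already the outcome before randomisation.

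**Direction.** Events that occur at the same rate in all groups, for reasons unrelated to the test, move the hazard ratio towards 1.

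**Size, as an illustration only.** Every input below is assumed except the group size. That is 2752 × 0.8 / 3 = 733.9, or about 734, from the planned elderly sample and the 20% dropout in Section 7.4. It counts all elderly participants, not only those on antibiotics. In the first row, switch times are exponential with mean 72 hours in the control group, the true hazard ratio is 1.3, and censoring is at 240 hours. A share f in both groups has an oral dose unrelated to any switch, after a mean of 6 hours. Results are from a Cox model over 100 simulated trials per value of f.

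| | f = 0 | f = 20% | f = 40% | f = 60% |
|---|---|---|---|---|
| Hazard ratio, true value 1.3 | 1.31 | 1.25 | 1.17 | 1.12 |
| Power, two-sided 5% | about 100% | 98% | 81% | 58% |
| Hazard ratio, true value 1.5 | 1.49 | 1.37 | 1.26 | 1.16 |

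The last row is a separate run with a median switch time of 72 hours, early events at 1 to 6 hours, and 20 simulated trials per value. The pattern is the same; the level depends entirely on f, which the documents do not give.

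**The case against.** **One unpowered endpoint among many.** Section 7.4 powers diagnostic accuracy, length of stay and isolation, not prescribing. The switch data are in the CRF, so a switch analysis could be added without changing conduct. This stands and limits the gravity of the point. It does not remove it: the protocol itself fixes the event and population of 1(b), so this is not a detail left open for an analysis plan.

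**First regimens are not always beyond the reach of the test.** Section 6.1.12 accepts that the study nurse may see a patient before medication is prescribed, and the near patient tests read in 10 to 15 minutes. Some Group 1 patients could therefore start on oral drugs because of a result. This also stands. It is why a new population must not be defined by treatment received after randomisation: that would remove patients whom the test spared IV drugs.

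**Readings that go further than the text.** A reader might infer three stronger faults.

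- *That 1(a) fails in the same way.* It times "Time, from admission to MAU, to first administration of 'narrow-spectrum' antibiotics". Its hypothesis speaks of earlier use, not of a switch, and time to first dose measures earlier use. A narrow drug added to continuing broad cover would count, so 1(a) does not measure streamlining, but that is not its stated aim.
- *That spectrum coding differs by study group.* Section 6.2.2, item 2, says the nature of the antibiotic, "whether 'narrow/targeted' or 'extended'-spectrum, will be entered subsequently in the CRF". The two words before the contrast read naturally as synonyms. Nothing ties the coding to a known pathogen or to study group.
- *That escalation is scored as benefit.* Section 1.5 mentions adjustment at 48 hours when there is no improvement. It does not describe failed oral or narrow treatment being escalated, and 1(b) ignores later changes; it does not credit them.

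**Conclusion.** The point holds for endpoint 1(b) and only there. The event is a first oral dose in anyone prescribed antibiotics; the hypothesis is a change of route from IV to oral. Patients who never had IV, and patients given an oral drug alongside continuing IV, are counted as events. Some of these events can fall before any result could act.

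The expected effect is dilution towards no difference, on the assumption that such events are mostly unrelated to study group. Its size cannot be derived from the documents; the hazard ratios above show a pattern on assumed inputs and are not an estimate for this trial. The three powered endpoints do not depend on this definition. Endpoint 1(a) agrees with its stated hypothesis.

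**What to change.** **Redefine 1(b)** in Section 7.5.1 and the Synopsis. Among patients on IV antibiotics at randomisation, it becomes the time to the first point at which all systemic antibiotics being given are oral and no IV dose follows for at least 24 hours. The 24 hours match the rule already used for fever and oxygen. Fixing the population at randomisation means a rapid result cannot affect who is included. Since nobody in this population can have the event before randomisation, patients should enter the risk set at that moment. Section 6.1.14 records the specimen collection time; if the CRF lacks the randomisation time, this is a usable stand-in, because it precedes any trial test result.

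**Keep time to first oral dose**, in all patients prescribed antibiotics, as a supporting analysis. It retains patients who start on oral drugs, including any whom a rapid result spared IV treatment.

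**Leave 1(a) as it is.** A supporting broad-to-narrow switch time, from the data noted in Section 4.1, would address streamlining.

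**Reconcile** administration (Section 7.5.1) with prescription (Section 7.6).

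**Cost.** Fewer patients contribute to 1(b), and a rule is needed for those discharged before the 24 hours have run. Otherwise the change is one of wording: treatment, route and times of change are already recorded under Sections 4.1 and 6.2.2, and no patient's care alters.

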#### 4 STUDY DESIGN

#### 4.1 Overall design

The study is a prospective, randomised controlled trial to evaluate the impact of rapid diagnostic testing for influenza, respiratory syncytial virus and *Streptococcus pneumoniae*, on the management and outcome of acute cardio-pulmonary admissions in the elderly (age  $\geq 65$  years), and 'high-risk' individuals (have underlying chronic heart or lung disease, including asthma) who are 18-64-years of age. Or Pneumonia / influenza type symptoms.

Patients who present to Medical Admissions' Units in Leicestershire with an acute exacerbation of chronic cardio-pulmonary illness of  $\leq$ 168 hours (7 days) duration, OR an acute cardio-pulmonary illness of  $\leq$ 7 days duration (including: pneumonia; 'influenza'/influenza-like illness; 'exacerbations of chronic obstructive pulmonary disease' (COPD); bronchitis; asthma; congestive heart failure; or cardiac arrhythmia), who satisfy the study inclusion and exclusion criteria (See Sections 5.2 and 5.3), and can be recruited to the study within a 16-hour period of initial assessment by a doctor on the Medical Admissions Unit or another ward accepting acute medical admissions, will be randomised to one of three groups:

Group 1: Rapid near patient diagnostic tests (influenza and pneumococcus), Group 2: Rapid molecular tests (influenza & RSV), plus laboratory pneumococcal antigen testing, and Group 3: Traditional 'laboratory culture' (influenza, RSV, and *S. pneumoniae*)]

All tests will eventually be done on all patients who enter the study, but patients in Groups 1 and 2 will only be provided with rapid test results relating to their randomisation group.

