#### 6.1.2 Approach to potential trial participants

Potential research participants will only be approached by the Study Nurse or Study Doctor after they have been admitted and assessed by the nursing staff on the Medical Admissions Unit or another ward that admits patients with acute cardio-pulmonary conditions, normally after they have been clerked by the admitting doctor. The Study Nurse (or Study Doctor) may approach an accompanying relative or carer of a referred patient who can not give signed informed consent either because: (a) he/she is so breathless or confused that he/she is temporally unable to assimilate information regarding the study to judge whether to participate; or (b) the patient has pre-senile or senile dementia. In such cases, the Study Nurse or Study Doctor will seek informed Assent from either the patient's relative or a carer. The Study Nurse or Study Doctor will subsequently approach patients whose recovery enables them to provide signed informed consent.

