#### 7.6 Statistical analysis

All analyses for both process and clinical outcomes will be based on Intention to Treat (ITT) analyses.

Impact of test result on prescribing The time to prescription of `narrow spectrum', `oral antibiotics' or `no antibiotics' between the three groups will be assessed using survival analysis techniques, whilst the use of neuraminidase inhibitors in those with influenza will be assessed using  $\chi^2$  tests, together with 95% CIs. Further analyses to allow for potential differences in patient demographics and baseline clinical characteristics between the three diagnostic test groups, and not allowed by stratification, will make use of cox proportional hazards regression modelling in the case of time to appropriate prescribing and logistic regression techniques in the case of neuraminidase inhibitors.

*Length of hospital stay* Length of hospital stay in the three diagnostic groups will initially be compared using non-parametric methods. Further analyses to allow for potential differences in patient demographics and baseline clinical characteristics between the three diagnostic test groups, and not allowed by stratification, will make use of generalised linear models in order to accommodate any skewness in the data.

*Mortality rates* Mortality rates between the three diagnostic testing groups will be compared by means of a Log-Rank Test and Kaplan-Meier survival curves. Adjustment for potential differences in patient demographics and baseline clinical characteristics between the three diagnostic test groups, and not allowed by stratification, will make use of Cox proportional hazards regression methods.

*Diagnostic accuracy* Sensitivity, specificity, positive predictive value of molecular and near patient diagnostic tests in comparison to traditional laboratory methods will be calculated together with 95% CIs. Heterogeneity in the sensitivity and specificity with respect to patient demographics and baseline clinical characteristics will be explored as secondary analyses using patient defined sub-groups.

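### Prescribing and isolation times start before randomisation, which dilutes the comparison; separately, endpoints 1(a) and 1(b) select patients on antibiotic prescribing that can follow allocation

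*Protocol*

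**What the plan says.** Protocol 7.5.1 item 1(a) is "Time, from admission to MAU, to first administration of 'narrow-spectrum' antibiotics, for patients in Groups 1, 2, and 3, who are prescribed antibiotics", and item 1(b) is "Time, from admission to MAU, to first administration of oral antibiotics, for patients in Groups 1, 2, and 3, who are prescribed antibiotics". Item 1(c), time to no antibiotics, also runs from MAU admission, but its set is different: "administered to patients in Groups 1, 2, and 3, who have influenza or RSV". Item 4(a) is "The time from admission to the MAU to the time of admission to a single room (isolation cubicle"), compared in patients with confirmed influenza or RSV. The synopsis repeats all four definitions.

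On the timing of entry, section 4.1 admits patients who "can be recruited to the study within a 16-hour period of initial assessment by a doctor on the Medical Admissions Unit". Section 6.1.2 says they are approached after admission, "normally after they have been clerked by the admitting doctor". Under 6.1.13 the study pack holding the allocation is opened only after consent is signed.

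Hypothesis 3 in section 2.1 concerns, among other things, "an earlier switch from intravenous to oral therapy". Section 7.6 states: "All analyses for both process and clinical outcomes will be based on Intention to Treat (ITT) analyses". No power is stated for any of these time-to-event endpoints; section 7.4 covers diagnostic accuracy, length of stay and the level of appropriate isolation.

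**The concern.** A rapid test can change management only after the patient has been allocated and a result reported. A first narrow-spectrum dose, a first oral dose, a stop of antibiotics or a move to a single room that happens earlier says nothing about the test. The endpoints as written count it all the same. Sections 6.2.2 and 6.2.3 call the relation of test results to antimicrobial therapy and to isolation key measures, so a diluted null here could be misread as evidence that rapid results do not change practice.

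The restriction in 1(a) and 1(b) raises a different problem. If a rapid result leads the team not to start antibiotics, that patient leaves the rapid arm's analysis set while a similar patient in the culture arm stays in. The two sets then no longer match as randomised.

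**Working it through.** **1. Order of events.** The clock starts at MAU admission (7.5.1). Then come clerking, approach (6.1.2), consent, and pack opening (6.1.13), up to 16 hours after the first medical assessment (4.1). Section 1.5 says empirical treatment cannot wait for conventional results. Section 6.1.15 records whether the patient is already in a cubicle when sampled. All four events can therefore precede allocation, and neither 7.5.1 nor 7.6 sets them aside.

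**2. Endpoint 1(b) against its hypothesis.** A patient started on oral drugs at admission has the event at once without ever having had intravenous therapy. Section 4.1 already requires the intravenous-to-oral switch to be noted, so the data for the intended measure exist.

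**3. The analysis set of 1(a) and 1(b).** Section 6.1.12 allows that the nurse may see the patient before anything is prescribed, so prescribing can follow allocation. The synopsis lists avoidance of antibiotics in influenza and RSV among the intended effects, so membership can depend on the arm. Neither evaluation population at the end of 7.3 is defined by antibiotic prescribing. Where antibiotics were prescribed before allocation, the restriction is a baseline feature and harmless.

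**4. Size of the dilution (illustration).** The protocol gives no figure to reproduce. Inputs:
- Whole elderly sample per group: 2752 × 0.8 / 3 = 734 (recruitment target and 20% dropout from 7.4). This is an upper limit for 1(a) and 1(b), because the number given antibiotics is not stated.
- Patients for 4(a): 92 influenza + 46 RSV = 138 elderly per group (7.1); × 0.8 = 110.
- Assumed: hazard ratio 1.2 after randomisation, and a share *f* of events before it.

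If nearly every patient eventually has the event, and pre-randomisation events have hazard ratio 1, the log hazard ratio on the admission clock is about (1 − f) ln 1.2, with ln 1.2 = 0.182. For two arms of n, two-sided 5%:
- from admission: power ≈ Φ(½√(2n) × (1 − f) × 0.182 − 1.96)
- from randomisation, in those still at risk: power ≈ Φ(½√(2n(1 − f)) × 0.182 − 1.96)

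At n = 734, f = 0.3 these are Φ(2.45 − 1.96) = 69% and Φ(2.92 − 1.96) = 83%.

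| n per group | f | from admission | from randomisation |
|---|---|---|---|
| 734 | 0.1 | 88% | 91% |
| 734 | 0.3 | 69% | 83% |
| 734 | 0.5 | 42% | 70% |
| 734 | 0.7 | 18% | 48% |
| 110 | 0.3 | 16% | 20% |
| 110 | 0.5 | 10% | 16% |
| 110 | 0.7 | 7% | 11–12% |

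Log-rank simulations with randomisation 2–16 h after admission, mean 48 h to event and follow-up to 240 h (all assumed) agree. At 734 per group they give 67–68% v 81–83% (f = 0.3), 38–42% v 68–71% (f = 0.5) and 17–19% v 46–54% (f = 0.7). At 110 they give 16/10/7% v 20/16/13%.

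A Cox simulation at an assumed hazard ratio of 1.5 gives about 1.41, 1.28, 1.16 and 1.08 on the admission clock at f = 0.2, 0.4, 0.6 and 0.8, and about 1.5 from randomisation throughout. The scaling rule gives 1.5^0.8 = 1.38, 1.5^0.6 = 1.28, 1.5^0.4 = 1.18 and 1.5^0.2 = 1.08.

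**5. Selection (illustration).** Suppose there is no true effect on timing, 15% of patients are viral cases (10% influenza + 5% RSV, from 7.1), and mean time to oral therapy is 12 h in viral and 60 h in other patients (assumed). Avoiding antibiotics in 20% or 50% of the rapid arm's viral cases moves that arm's median from about 33 h to 34.7 h or 37.0 h. The apparent delay comes only from who is left in the set; other assumptions could reverse its direction.

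**The case against.** The strongest reply is that time from admission is a coherent policy measure, also used for fever and oxygen in 7.5.1. It keeps every patient in the allocated arm, and early events are balanced by randomisation. That stands: the test is valid under the null and loses only power. A reader might infer that the admission clock itself breaks intention to treat; it does not.

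A reader might also infer that the isolation endpoint or 1(c) is limited to antibiotic recipients. Both cover patients with influenza or RSV. That is an infection state at entry and a different matter, provided it is ascertained alike in all arms.

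It is equally tempting to say that patients whose antibiotics are avoided disappear from the trial. They leave 1(a) and 1(b) only: 1(c) covers influenza and RSV patients without that restriction, and 7.5.2 item 3(a) costs avoidance in all patients.

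Many patients will probably have been prescribed antibiotics before allocation, which limits the selection problem. It does not remove it, because 6.1.12 foresees later prescribing. It also increases the scope for early events under the first fault.

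Finally, no stated power rests on these endpoints, and a sensitivity analysis from randomisation would need no endpoint change. That is a fair minimum, but it would leave the diluted version as the defined endpoint and 1(b) not measuring its hypothesis.

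**Conclusion.** Both faults hold, within limits. The early clock affects 1(a), 1(b), 1(c) and 4(a). It attenuates the contrast and costs power; it creates no bias under the null. Endpoint 1(b) also misses the intravenous-to-oral switch it is meant to capture. The antibiotic restriction affects 1(a) and 1(b) only, matters only for patients not yet prescribed at allocation, and there conflicts with the intention-to-treat statement.

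The protocol does not allow the size to be computed: the share of early events, the hazard ratio, the event time and the delay are all assumptions. The 16-hour limit runs from initial assessment, not from admission. Under the illustration, the loss is small at a 10% share and large at 50% or more. For 4(a) the gain from changing the clock is only a few points, and power stays very low either way. The direction of the dilution does not depend on these inputs. The change is worth making because it is cheap and concerns measures the protocol itself calls key.

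**What to change.** Time 1(a), 1(b), 1(c) and 4(a) from randomisation. Record the time the pack is opened; specimen time, already in the CRF (6.1.14), is a close proxy. Replace the antibiotic restriction with sets defined by status at that moment:
- 1(a): on antibiotics, not yet narrow-spectrum
- 1(b): on intravenous antibiotics, not yet oral
- 1(c): influenza or RSV patients then on antibiotics
- 4(a): influenza or RSV patients not already in a single room

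Tabulate by arm the patients who already had each event. For patients not yet on antibiotics at randomisation, report by arm the proportion later prescribed any, so that avoidance is counted. Treat death as a competing event throughout, and stopping all antibiotics as a competing event for 1(a) and 1(b) only; in 1(c) it is the event itself, and it has no bearing on 4(a). Keep the admission-clock version as a secondary policy measure.

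The cost is endpoint wording, analysis code and one added time field. Drug times and routes (6.1.12, 6.2.2) and initial isolation status (6.1.15) are already collected. The analysis sets become smaller, but patients who already had an event carry no information on the test's effect on that event.
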